Study Design	Open label comparison of two proven interventions in COPD to assess responsiveness of exercise tests
Study Participants	Adult COPD subjects
Planned Sample Size	 Phase 1, n=60 (to allow for drop out & interim analysis after the last visit of patient #50) Phase 2, further 79 (allowing for a 25% drop out) Total recruitment of 139 subjects
Follow-up duration	Six weeks
Planned Study Period	17 Months – Phase 1 (March 2013 – December 2014) 24 Months – Phase 2 (December 2015 – November 2017)
Aims	To assess the responsiveness of a range of exercise tests in relation to six minute walk
Outcome measures	ISWT, ESWT, 6MWT, endurance cycle, incremental cycle, SPPB, PROactive, Accelerometery.

Aim

By conducting a comprehensive comparison of exercise tests commonly employed to assess functional capacity in subjects with COPD we aim to secure a wider understanding of the relative properties (stability and sensitivity) of the these tests to guide clinical trial outcome selection. The study will produce data which are sufficiently robust to provide information for the regulatory bodies regarding the assessment of activity limitation in COPD for future clinical trials.

Hypothesis

The 6MWT is the least sensitive test that can be employed in the assessment to response to treatment of either pulmonary rehabilitation or bronchodilator therapy.

Background

Exercise outcomes are required to capture outcomes relevant to subjects missed by spirometry

Traditional measures of airflow obstruction such as FEV_1 offer an inadequate reflection of the impact of COPD and are not influenced by otherwise effective therapy, particularly pulmonary rehabilitation (1, 2). Conversely exercise tests are used to assess activity limitation (disability) and are capable of improvement after various therapies, including bronchodilators (3). Several exercise tests have been described for this purpose. The existing tests vary in the required physical environment (laboratory vs. field), exercise platform (cycling vs. walking) or protocol (maximal vs. endurance, paced vs. self-paced). There has been no comprehensive comparison of the relative reproducibility and sensitivity of these tests when performed concurrently.

Existing tests span a range of complexity

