Subjects (approximately, to allow for withdrawals) will be recruited from clinics, trial registers and pulmonary rehabilitation (PR) waiting lists along with subjects identified from primary care COPD registers and poster response from displays at GP practices and hospitals. Subjects will be randomised to one of 3 groups (control:PR:LAMA) in a 1:2:2: allocation for phase 1 and a 1:1:4 for phase 2 of the trial. The aim will not be to evaluate the interventions but simply to produce a range of change in performance so that the changes in the exercise tests employed can be evaluated. The five most commonly reported exercise tests, strength testing and the Short Physical Performance Battery will be examined at baseline and after 6 weeks of the intervention or control period. The outcome measures will be conducted by blinded assessors. A planned analysis will be conducted after the 50th patient's last visit to confirm that commitment of the full resource and the 'opening' of other sites will deliver the desired data.

Eligible participants

The subjects will have a confirmed diagnosis of COPD and have GOLD stage 2-4 disease, and MRC grade dyspnoea2 or greater. Participants will be restricted to 40-85 years, so that they align with the 'classic' COPD patient. Since the aim is to compare different exercise outcomes, participants will not be stratified by exercise performance at baseline. However review of two sites (Leicester and RBHT) entrants to pulmonary rehabilitation programs suggests, based on ISWT data, that ~80% of participants will have an 6MWT <350m¹.

Exclusion criteria

Participants will be excluded from the trial if they have co-morbidities that limit the ability to walk/cycle, for example musculo-skeletal, arthritic, or neurological disorders. Common COPD co-morbidities such as controlled hypertension or heart failure will not be excluded, but will be documented. Since rehabilitation

¹ For example of 173 consecutive subjects in a currently submitted MS from Harefield the 75th centile for ISWT was 283m.

is one of the interventions, subjects who have participated in rehabilitation over the last 12 months will also be excluded, simply because they may not then gain additional benefit. Participants using LTOT therapy will also be excluded as will those requiring oxygen therapy during the course of an exercise test (i.e. desaturation documented below 85%)

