For this study we considered, first, that it was important not to have a falsely low sample size and second that most of our subjects would be receiving a LABA. We therefore selected the figure generated by Fernandes paper, of 128 subjects per group but reduced the size of the whole group by 2:2:1 allocation giving a total sample size of 320. The calculation has been reviewed by statisticians from both GSK and Novartis who suggested an interim analysis because of the large range of potential values obtained.

Data entry will be managed by the Leicestershire CTU and held on a secure database. At a pre-agreed time the data will be released to the investigating team, this will be upon completion of the initial baseline measures to explore the stability of the measures and final data release upon completion of the intervention arms of the study. There will is a planned interim data analysis during the intervention phase, after the LV of patient #50. The analysis plan will be pre-defined as described below. There will be a pre-planned sub group analysis on participants with a baseline 6MWT test performance of less than 350m.

Pilot study.

Over the first twelve months a pilot (feasibility) study will be conducted at a single centre (Leicester). Sixty subjects will be recruited allowing for a drop out of 10 and analysis of 50 subjects completing the intervention period & attending all visits; subjects will be randomised and followed up after randomisation to either intervention. The procedure will be as outlined above.

The analysis of this pilot data will be supported by statisticians from Novartis. Preliminary data will be used to confirm the initial power calculations.

For the pilot study web based randomisation, data entry and monitoring will be managed by the Leicester Clinical Trials Unit. The database will be developed to support the multi-centre trial.

Sample Size re-estimation following Pilot Study & Interim Analysis

Upon collection and analysis of interim data, the ESWT was chosen as the exercise measure to recalculate sample size requirements for phase 2. This measure showed high repeatability at initial visits and sensitivity to change within treatment relative to a suggested MCID of 45-85 seconds*. Interim results for ESWT reported a change from baseline of 59 seconds (SD=163 seconds) for the LAMA arm.

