
Based on the interim results, approximately 90 evaluable subjects in the LAMA arm are required to provide >80% power to detect a 50sec change from baseline, assuming a standard deviation of 160sec and a one-sample, two-sided t-test at a significance level of 0.05. To account for a potential 25% dropout rate in Phase 2, 120 subjects will be randomized to the LAMA treatment arm.

The table below shows the number of evaluable subjects needed from the LAMA arm in Phase II to detect a 50 second change from baseline at either 80% or 90% power, given different estimates of standard deviation.

Table of one sample t test power to acted sosse change from baseline					
N needed	SD = 130	SD = 140	SD = 150	SD = 160	SD = 170
Power =80%	56	64	73	83	93
Power =90%	73	85	97	110	124

 Table 3. One-sample t-test power to detect 50sec change from baseline

As changes from baseline are not expected in a control arm, and pulmonary rehabilitation has demonstrated effects in all exercise measures in the interim analysis, these arms will serve mainly to provide additional study sensitivity data. Thus, the randomization allocation will change from 2:2:1 to 4:1:1 to make sufficient within-group comparisons. 30 subjects will be randomized to receive pulmonary rehabilitation and 30 subjects will be randomized as controls in order to provide 22 additional evaluable subjects, plus 8 more to account for a potential 25% dropout rate, in each arm. In total, 180 subjects will be randomized to Phase 2.

2. Sample size re-estimation

WP4 Exercise outcome study

The revised power calculation is aligned with the actual data from the interim analysis. This new calculation is based on a mean change in the ESWT of 60±160 seconds (as per interim analysis) with 80% power and alpha of 5%. A total of 58 subjects are required in the LAMA group and allowing for 25% attrition, a total of 78 recruited subjects are required in the LAMA (table 4). As stated above there is no specific target allocation for placebo or PR in phase 2. We propose to maintain the control arm to provide a negative control to the LAMA arm and reduce the study bias, and allow us to maintain blinding.

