Table 4: One-sample t-test power to detect 60sec change from ba	seline
---	--------

N needed	SD = 130	SD = 140	SD = 160
Power =80%	39	45	58

Randomisation allocation recruitment at Glenfield hospital, Leicester, can be seen in Table 5 (April 2015 – September 2016).

Allocation and Ratio	Control	PR	LAMA
1.2.2 (actual)	16	32	32
1.1.4 (actual)	2	2	10
Current allocated totals	18	34	42
Number required for LAMA (ESWT response of 60±160 sec with 80% power and alpha of 5	-	-	78 recruited 58 completed
New allocation for recruiting n=78 in LAMA (1:0:4)	9	0	36
Total recruited to trial	27	34	78

Table 5: Randomisation allocation over	er time
--	---------

To ensure rigor is maintained a randomisation allocation of 1:0:4 would recruit a further 9 subjects to the control group and a further 36 into the LAMA group.

Analysis Plan

All exercise test data will be analysed on a per protocol basis. All data will be assessed for normality and analysed using appropriate parametric or non-parametric statistics. Significance will be set at p<0.05 and differences will be expressed as mean and standard deviations (SD) or 95% confidence intervals.

Data will be presented as mean (SD) or median (IQR). Comparison of values obtained within the treatment(s) and the control groups will be made using a paired t test or the Wilcoxon signed rank test. All tests will be 2 tailed. Additional analysis will be done to determine the sensitivity and specificity of the other measures to detect the change in MCID. Similarly the sensitivity and specificity of the failure to detect change in the placebo will also be determined.

Reproducibility study – The baseline data will examine the test-re test reproducibility of each of the tests employed, including measures of strength. The primary variable for each test will be the conventional measure of performance. Data will be compared in two ways, firstly the intra-class correlation (ICC) will be reported and secondly limits of agreement using Bland & Altman techniques (41). The Bland & Altman plot will allow us to check the data for stability across a range of performance.

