Sensitivity study - Comparison between the exercise test outcome measures will be made at two separate time points, baseline and 6 weeks. The primary measure for each test will be the variable that is most commonly reported e.g. distance /time/peak oxygen consumption. We will assume that an MCID of 25m is meaningful for 6MWT (15), and assess the ability of other tests to predict this change. Attention will be paid to both floor and ceiling effects.

Data accumulated from individuals offered rehabilitation upon completion of either the control or LAMA arm will be analysed after the main trial has been completed. This data will allow a repeat measures analysis comparing the relative effect of two interventions upon the exercise tests. This is a secondary planned analysis.

Opportunities for sub studies

a) MCID - This study would afford the opportunity to test this assumption and identify an MCID for the exercise tests employed in this study. We will report the MCID in one of two ways, we will employ an anchor based approach and report a statistically general distribution based approach. In addition by relating observed changes in exercise performance to the CRQ we will aim to generate a further MCID for the exercise tests, since it has recently been suggested that an MCID may differ depending on the context and nature of the intervention (37).

Practical Considerations & timescale to do (plus Gant chart)

Three sites should be adequate to recruit the required number of subjects. We estimate that it would take 36 months to complete this study, the pilot study will be conducted over the first year with a recruitment target of n=50. After this pilot phase recruitment will be extended to 3 sites.

Pilot study

Allow 3 months to gain necessary recruitment approval, advertise and recruit staff. To confirm whether MHRA approval required. Completion of ethics submission.

Months 1-3	Finalise ethics approval/set up database & randomisation system with Leicester & staff training as required.	
Month 3-24	Recruit 50 subjects to study – completion of baseline measures	
Month 24-30	Completion of data collection and preliminary analysis	
Month 24-30	Change ethics for multi-centre study	
Month 30-33	Recruitment in place for other sites (2/3)	

Study extension (planned recruitment – 180 participants – 90 per site). Recruitment will continue seamlessly at the Leicester site but allow for 21 months recruitment from the end of the pilot data).

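### The protocol's current text gives conflicting Phase 2 allocation ratios, sizes and control shares, and presents rounded planning values as the interim result

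*Protocol*

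**What the plan says.** **Allocation.** The Method section describes randomisation to three groups, control:PR:LAMA, "in a 1:2:2: allocation for phase 1 and a 1:1:4 for phase 2 of the trial". The first re-estimation (Sample Size re-estimation following Pilot Study & Interim Analysis) agrees, listing the arms in the opposite order: "the randomization allocation will change from 2:2:1 to 4:1:1 to make sufficient within-group comparisons". After the second re-estimation, Table 5 shows 80 subjects allocated at 1:2:2, 14 at 1:1:4 and a new ratio for the rest: "To ensure rigor is maintained a randomisation allocation of 1:0:4 would recruit a further 9 subjects to the control group", with 36 more to LAMA and none to PR.

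**Phase 2 size.** The synopsis has "Phase 2, further 79 (allowing for a 25% drop out", for a total of 139. The first re-estimation randomises 180 to Phase 2. The section Practical Considerations & timescale has "Study extension (planned recruitment – 180 participants – 90 per site".

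**PR and control numbers.** The first re-estimation says "30 subjects will be randomized to receive pulmonary rehabilitation and 30 subjects will be randomized as controls". The second, directly below it, says "As stated above there is no specific target allocation for placebo or PR in phase 2". Intervention 3 (control group/usual care) puts one quarter of recruited subjects in control.

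**Interim inputs.** The first re-estimation states "Interim results for ESWT reported a change from baseline of 59 seconds (SD=163 seconds) for the LAMA arm". The second uses 60 s with SD 160 s and attributes those values to the interim analysis. From them it derives 58 completers and 78 recruited in the LAMA arm, at 80% power and 5% alpha.

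**The concern.** All of these statements stand in current text; none comes from an amendment log. Whether PR remains open to new patients is a basic design fact, and the Method section and Table 5 answer it differently. The two Phase 2 sizes differ by more than a factor of two (180 against 79).

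The LAMA target of 78 depends on which ratio is used for the remaining recruitment, and the 80% power depends on which pair of ESWT values is taken as the interim result. A reader of the final report who wants to know what was planned, and with what power, cannot settle either from the protocol as it stands.

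**Working it through.** **1. Reproduce the stated sample size.** Inputs from the second re-estimation: change 60 s, SD 160 s, two-sided 5%. The one-sample t-test is named in the first re-estimation and in the title of Table 4. Power comes from the noncentral t distribution with n − 1 degrees of freedom and noncentrality (change/SD) × √n.

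- n = 58: 60/160 × √58 = 2.856; critical t = 2.002; power 80.2%. 58 is the smallest n that reaches 80%.
- 58/0.75 = 77.3, so 78 recruited.

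Tables 3 and 4 reproduce in full by the same method. The calculation is correct for its own inputs.

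**2. Use the interim values as reported (59 s, SD 163 s).**

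- n = 58: 59/163 × √58 = 2.757; power 77.3%.
- n = 61 gives 79.4% and n = 62 gives 80.1%, so 62 completers would be needed for 80%.
- The normal approximation at n = 58 gives 78.7%, but the protocol specifies a t-test.

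**3. Rebuild Table 5.**

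| Period | Control | PR | LAMA | Total |
|---|---|---|---|---|
| 1:2:2 | 16 | 32 | 32 | 80 |
| 1:1:4 | 2 | 2 | 10 | 14 |
| 1:0:4 (new) | 9 | 0 | 36 | 45 |
| All | 27 | 34 | 78 | 139 |

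The table is internally consistent and its total agrees with the synopsis.

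**4. What the ratio changes, with the total held at 139.**

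- Table 5's last 45 put back to 1:1:4: 45 × 4/6 = 30 LAMA, so 42 + 30 = 72. At 25% attrition, 72 × 0.75 = 54 completers. Power is 77.2% at 60/160 and 74.3% at 59/163.
- Adding 36 LAMA at 1:1:4 would take 36 × 6/4 = 54 subjects, not 45.
- Method ratios with the synopsis split: 60 × 2/5 + 79 × 4/6 = 24 + 52.7 = 76.7, about 77 LAMA. At 25% attrition that is about 57 completers, with 79.5% power at 60/160.

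**5. Phase boundary.** The synopsis has 60 in Phase 1 and 79 in Phase 2. Table 5 has 80 at 1:2:2, then 14 + 45 = 59. So 80 − 60 = 20 subjects beyond the Phase 1 target were allocated at the ratio that the Method section reserves for Phase 1.

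**6. Control share.** 1:2:2 gives 1/5, 1:1:4 gives 1/6 and 1:0:4 gives 1/5. Overall, 27/139 = 19.4%. None is one quarter.

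**The case against.** The second re-estimation calls itself revised and new, and Table 5 is titled as allocation over time, with rows marked as actual or new. A careful reader can therefore see that 1:0:4 is the working instruction and that 90/120/180 belong to an earlier step. Randomisation is computerised and, for the pilot, managed by the trials unit, so sites do not apply a ratio read from the Method section. This stands: a reader might infer that sites would go on randomising to PR, and the documents do not support that.

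A reader might also infer that the Method ratio by itself yields 72 LAMA. It does not. That figure needs Table 5's counts to date with only the last 45 put back to 1:1:4; the Method ratios with the synopsis split give about 77, close to the target.

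Rounding 59/163 to 60/160 is mild. If about 20 of the 50 interim subjects were on LAMA (an assumption, from the 2/5 share), the standard errors are about 163/√20 = 36 s for the mean and 163/√38 = 26 s for the SD, so 1 s and 3 s are well within noise. The power difference is 2.7 points below 80% by the exact t-test and 1.3 by the normal approximation. This also stands, and it limits the point to the label and the stated power.

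A reader might further object that moving the target from 50 s to 60 s hides a loss of power. Tables 3 and 4 largely show the cost: at SD 160 s and 80% power, 83 completers for 50 s and 58 for 60 s. The 60 s target also lies within the cited MCID range of 45 to 85 s, so asking for power at 45 s would be a preference.

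What the objection leaves untouched is the uncorrected Method ratio, the 180 in the timescale, the denial of a target directly after 30 and 30, and the control quarter.

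**Conclusion.** The point holds as a failure to reconcile current text. The allocation and Phase 2 size conflicts are the serious part: 1:1:4 against 1:0:4 for the last 45 subjects, and 79 against 180. The PR and control target and the control share (one quarter against about one fifth) are plain contradictions of smaller weight.

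The sample size of 58 completers and 78 recruited is arithmetically right for 60/160. What is wrong is calling those values the interim result: at the reported 59/163, power with 58 completers is about 77%. Both roundings are favourable, but the shortfall is small and does not show that the arm is too small.

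The LAMA shortfall depends on the reading: 72 if Table 5's remaining 45 went back to 1:1:4, about 77 under the Method ratios with 60 + 79. Both hold the total at 139. The completer counts assume 25% attrition, and the power figures assume the exact two-sided one-sample t-test.

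**What to change.** - In the Method section, state the three allocation periods in Table 5 (control:PR:LAMA): 1:2:2 for the first 80, 1:1:4 for the next 14, 1:0:4 for the last 45. Say plainly that PR receives no further allocation in the last period.
- Reconcile these periods with Phase 1 = 60 and Phase 2 = 79, explaining that 20 subjects beyond the Phase 1 target were allocated at 1:2:2.
- Mark the 90/120/180 figures and the 30 PR and 30 control as superseded by the second re-estimation, and remove the reference back to an absent target.
- Correct the timescale to 79 in Phase 2 (139 in total), and its per-site figure with it.
- Correct the control share under Intervention 3 to about one fifth.
- Describe 60 s and SD 160 s as planning values rounded from the interim 59 s and SD 163 s, and state that 58 completers give about 77% power at the unrounded values.

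The cost is protocol wording and a slightly less favourable power statement. No extra recruitment is needed, and power at 45 s need not be added.

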Subjects will perform a maximal symptom-limited incremental exercise test on an electrically-braked cycle ergometer (ramp protocol, increments 10Watts/minute) and an endurance cycle test conducted at 85% of peak workload. Ventilation and gas exchange measurements will be made throughout the exercise tests using a breath-by-breath computerised system³. Initial, end-exercise, 3 minutes recovery and during loaded testing (every 2 minutes), the Borg breathlessness Score, RPE Score will be recorded along with reason for termination.. The same variables will be collected pre and post intervention/control periods and iso-time data with respect to peak performance measures on the initial assessment will be reported on post intervention measurements. All inhalers will be withheld for 6 hours prior to measurements. Other medications will remain unchanged. The variables reported from these laboratory based tests will be those conventionally reported and will include peak workload (watts), peak oxygen uptake (ml/min/kg) and ventilation (l/min). For the endurance test, exercise time will be an additional important outcome (secs). Prior to, upon completion and 3 minutes into recovery of laboratory testing, measures of HR, percutaneous oxygen saturation and BP will be recorded. Patient's safety and termination of testing will be conducted in accordance with ATS/ACCP (23).

2. Field based

Prior to and upon completion of the field based tests, measures of breathlessness, perceived exertion (Borg scores), HR, BP, and percutaneous oxygen saturation will be recorded. In addition the reason for termination (leg fatigue, SOB or combination) will be reported.

² http://publications.nice.org.uk/chronic-obstructive-pulmonary-disease-cg101

³ Glenfield uses a Medisoft ergocard gas analyser and Expair Software.

- 6 MWT this will be conducted along a 30 or 50m corridor according to the ATS guidelines (24). Encouragement will be standardised and a practice walk completed. Conventionally the output from the 6MWT is expressed in metres. We will record the number and duration of any breaks in walking taken by the patient. A total of 3 tests will be required (1 at visit 1 and 2 at visit 2) in order to test repeatability following familiarisation, before intervention.

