Six week supervised course of pulmonary rehabilitation. Participating centres will have access to existing established rehabilitation programmes. The rehabilitation programmes across the sites will follow recommended practice as defined in the ATS/ERS guidelines (36). The programme will extend over 6 weeks, twice a week. Each session will be 2 hours long, one hour allocated to exercise training, and the second hour is educational. The exercise regime will be a combination of aerobic and resistance training. The aerobic exercise will conform to the ATS/ERS guidelines (36). The Intensity will be at least 60% (ideally 80%) of the speed or peak workload achieved during the maximal walking and cycling exercise tests; the target duration will be 30 minutes, 5 times a week. This of course requires a home exercise programme that mirrors the training programme at the rehabilitation programme; this will be monitored with a home training diary.

Intervention 3 (control group/usual care)

This is a usual care control group, individuals will continue with their usual medication. At the end of the six weeks the six exercise tests will be conducted in random order. Since the aim is to evaluate the relative effect of change on different outcome measures only $1/4^{th}$ of the subjects recruited will be randomised to control therapy as a usual care group.

Testing procedure

The exercise tests will be presented in random order acknowledging the inter relationship between the tests for example an incremental test needing to be completed prior to an endurance test; however for each individual patient subsequent post intervention testing will be done in the same order as pre intervention testing at visits 2 and 3⁵. The exercise tests will be conducted by a blinded assessor, blinded to the prior exercise performance and the intervention. The assessors will be experienced in conducting CPET and laboratory based exercise tests, the same assessors will conduct all the tests at each site. The time of day will be recorded and repeat visits will be arranged at a similar time (am or pm). Ambient temperature (controlled by air conditioning), pressure (via the Meterological office website), date and season will be recorded in the data set.

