- b. 6 MWT (performed twice with a 30 min rest in-between)
- c. ISWT (performed twice with a 30 min rest in-between)
- d. Strength testing (QMVC)

Visit 3 (next day)

Three exercise tests will be conducted in random order. There will be at least 30 minutes rest between each test.

- e. ESWT (85% peak performance)
- f. Cycle endurance test (85% peak performance)
- g. SPPB

Retesting after completion of the 6 week intervention (visits 4 and 5), will comprise the following measures presented in the same order as baseline (visits 2 and 3). These tests will be completed by a blinded assessor, blind to the intervention and previous results. Two activity monitors will be given, to be worn during visits 4 & 5 and for a further 7 days (24 hours a day).

- 1. ISWT
- 2. 6MWT
- 3. ESWT, at same level as baseline
- 4. Maximal incremental cycle test
- 5. Endurance cycle test, at same workload level and RPM as baseline
- 6. SPPB
- 7. Strength testing (QMVC)
- 8. Health Questionnaires

At the completion of the interventions a global rating scale of change will be reported for each exercise test. This will allow the description of the MID using anchor and distribution based methods. The global rating scale will identify two levels of change (a little improvement and a greater level of improvement). The scale employed will be one recently described by Pepin et al (37) describing the MCID for the ESWT.

Power calculation

In order to calculate a sample size a literature search was conducted using the search terms Tiotropium and six minute walk (and variants e.g. 6MWT) to identify studies giving an estimate of the likely benefit of the drug. Results found are shown in Table 1.

n	Blinded Assessor	Baseline 6MWT (mean (SD))	Tiotropium 6MWT (mean (SD))	Reference	notes
30	n	344 (105)	363 (98)	Fernandes 2010 (38)	Additional use of LABA
38	У	490 (67)	+6 (19)	Oga 2000 (12)	Additional use of Oxitropium
41	n	403 (20)	429 (17)	Fujimoto (39)	-
38	n	222 (5)	+13.5 (2)	Um(40)	-
44	У	415 (75)	429 (70)	Okudan(21)	Single dose (after 120 minutes)

Table 1: Properties of trials investigating Tiotropium with the 6MWT.

Based on these data [name] (Statistician to the Royal Brompton hospital Biomedical Research Unit) estimated the following sample sizes for achieving an increase in 25m in 6MW with 80% power and p=0.05.

Reference	Tio 6MWT (SD of Change From BL)	Estimated Sample size
Fernandes 2010	100 *	128
Oga 2000	19	7
Fujimoto	20 *	7
Um 2007	2	1
Okudan 2006	75 *	73

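### Iso-time is anchored to the peak of the initial cycle test, so a patient whose follow-up test is shorter has no measurement at that time

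*Protocol*

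**What the plan says.** The rule is in the Method section of the protocol, under the laboratory exercise tests: "iso-time data with respect to peak performance measures on the initial assessment will be reported on post intervention measurements". It covers the incremental ramp test and the constant-load endurance test, both on the cycle.

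Four other statements bear on it:

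- Gas exchange is continuous: "Ventilation and gas exchange measurements will be made throughout the exercise tests using a breath-by-breath computerised system".
- Symptom scores are intermittent: "Initial, end-exercise, 3 minutes recovery and during loaded testing (every 2 minutes), the Borg breathlessness Score, RPE Score will be recorded".
- The follow-up endurance test repeats the baseline load: "Endurance cycle test, at same workload level and RPM as baseline". Equal elapsed time therefore means equal load.
- Under Testing procedure, the assessor is "blinded to the prior exercise performance and the intervention".

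Both cycle tests are done at Visit 1, labelled familiarisation. They are repeated at the baseline visits (incremental at Visit 2, endurance at Visit 3) and again at Visits 4 and 5. The Analysis Plan, under the sensitivity study, compares tests on the measure most often reported for each, with distance, time and peak oxygen consumption as examples. Iso-time is not named there.

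**The concern.** Iso-time analysis compares physiology and symptoms at the same elapsed time, and here the same load, before and after treatment. That requires a time reached in both tests. The protocol fixes the time from one test only, the earlier one. Whether a follow-up value exists then depends on whether the patient lasted at least as long as before, which is itself a response to the intervention.

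If iso-time results were reported on available values alone, each arm would be represented by patients who did not worsen. The control arm is kept as a negative control, and there a selected subset could show an apparent response. The trial aims to describe how tests behave for regulatory use, so this is worth preventing even in supportive data.

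The term initial assessment adds a smaller uncertainty, because it could mean Visit 1 or the baseline visits. For patients withdrawn from a LAMA before baseline, Visit 1 falls before the washout. The endurance load may also differ between Visit 1 and Visit 3.

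**Working it through.** **The plan's own figure.** The protocol gives no number for iso-time. The nearest relevant figures are those behind the LAMA sample size: a 60 s change in the endurance shuttle walk test (ESWT), SD 160 s, 80% power, two-sided 5%, one-sample t-test.

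- Normal approximation: (160 × (1.960 + 0.842) / 60)² = 55.8.
- Noncentral t: 57.8, rounded up to 58, as stated.
- With 25% attrition: 58 / 0.75 = 77.3, rounded up to 78, as stated.

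These figures reproduce, and iso-time plays no part in them.

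**Share of patients with a shorter follow-up test.** The protocol gives no distribution for change in cycling time. I assume that endurance-cycle time changes as the ESWT does and that the change is normal. The share is then Φ(−mean/SD).

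| Assumed change | Source | Share shorter | Of 58 |
|---|---|---|---|
| 60 s, SD 160 s | planning values | Φ(−0.375) = 35.4% | 20.5 |
| 59 s, SD 163 s | interim LAMA result | Φ(−0.362) = 35.9% | 20.8 |
| 60 s, SD 130 s | lowest SD in Table 4 | Φ(−0.462) = 32.2% | 18.7 |
| 120 s, SD 160 s | assumed | Φ(−0.75) = 22.7% | 13.1 |
| 180 s, SD 160 s | assumed | Φ(−1.125) = 13.0% | 7.6 |
| 0 s, SD 160 s | no change expected in controls | Φ(0) = 50% | – |

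The interim input is the reported "change from baseline of 59 seconds (SD=163 seconds) for the LAMA arm". The zero mean for controls follows the protocol's statement that no change is expected in that arm. The SD of 160 s for controls is assumed, but the 50% does not depend on it.

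**Possible shift in a complete-case iso-time mean.** Let r be the correlation between change in exercise time and iso-time response. The protocol does not give it, so I take 0.3 to 0.7. The shift, in SDs of the iso-time response, is r × φ(mean/SD) / Φ(mean/SD).

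- LAMA: φ(0.375)/Φ(0.375) = 0.372/0.646 = 0.576. The shift is 0.17 SD (r = 0.3) to 0.40 SD (r = 0.7).
- Control: φ(0)/Φ(0) = 0.399/0.5 = 0.798. The shift is 0.24 to 0.56 SD.

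**Incremental test.** The proxy should not be carried over to it. On a ramp of 10 W/min, an SD of 160 s would be 160/60 × 10 = 26.7 W, which nothing in the protocol supports. The same logical gap exists for that test, but I put no number on it.

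**Symptom scores.** Breath-by-breath data can be read at any time that the patient reached. Borg and RPE scores cannot. Except by chance, no scheduled score falls at another test's end time, and the last scheduled one can be almost 2 minutes earlier.

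**The case against.** The strongest reply is that the selection is inferred. The protocol does not say that patients with shorter follow-up tests are dropped. An end-exercise value could be carried to iso-time, or the shorter test's time used, and such rules are commonly left to a statistical analysis plan, which is not shown here. This stands in part: exclusion cannot be asserted. But the point is not a missing rule. The protocol states the reference time, and that time does not exist in a shorter follow-up test. Carrying a value forward is not a measurement at that time, and using the shorter test departs from the stated anchor.

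A reader might infer more than the protocol supports in three ways:

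- That iso-time results would come from improvers only. Patients with unchanged duration also have a value, so the group is those whose test was not shorter.
- That the laboratory tests would look more responsive than the field tests. The planned comparison rests on each test's primary measure, and peak and time outcomes exist however short the test.
- That the bias can be read from truncated mean times. Under the planning values, patients with tests not shorter average 60 + 160 × 0.576 = 152 s, against 60 s overall. Exercise time is observed in everyone, so this is not a bias in any reported result.

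Two further replies are fair. The 2-minute spacing affects only Borg and RPE, and the nearest reading is within 1 minute while loading continues. Context also favours the baseline visits as the meaning of initial assessment, because follow-up repeats the baseline order and load. Blinding does not prevent iso-time from being derived afterwards from recorded data.

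**Conclusion.** The point holds within a narrow scope. The stated anchor leaves patients with a shorter follow-up cycle test without a measurement at iso-time, and a complete-case comparison would be selected towards patients who did not worsen.

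For the endurance cycle test, roughly 35% of LAMA patients and 50% of controls would be affected, with a range of about 13% to 50%. These shares rest on a walking test standing in for cycling time and on a normal distribution. The shift in SD units also rests on an assumed correlation. Only the supportive iso-time data from the two cycle tests are concerned. The conclusions on the primary measures, the field tests, the sample size and the laboratory-versus-field comparison do not depend on it.

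**What to change.** In the Method section, under the laboratory tests:

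1. Define iso-time, per patient and per test, as the end of the shorter of the baseline test (Visit 2 incremental, Visit 3 endurance) and the matching test at Visit 4/5.
2. Read ventilation and gas exchange at that time in both tests.
3. Read Borg and RPE at the last scheduled 2-minute reading common to both tests.
4. Replace initial assessment with the named baseline visit.

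The cost is a few lines of protocol text and some programming. No new measurement is needed, and assessors stay blinded. For patients whose follow-up test is not shorter, the gas-exchange time is still the end of the baseline test. For the others, iso-time falls earlier in exercise. Borg and RPE have no loaded common reading if either test lasts under 2 minutes, and the number of such patients should be reported. Truncating every variable to a 2-minute mark would be simpler, but it would discard usable breath-by-breath data.
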